# 9. ADVERSE EVENTS (AE) AND SERIOUS ADVERSE EVENTS (SAE)

The investigator or site staff will be responsible for detecting, documenting and reporting events that meet the definition of an AE or SAE.

# 9.1. Definition of an AE:

Any untoward medical occurrence in a patient or clinical investigation subject, temporally associated with the use of a medicinal product, whether or not considered related to the medicinal product.

Note: An AE can therefore be any unfavorable and unintended sign (including an abnormal laboratory finding), symptom, or disease (new or exacerbated) temporally associated with the use of a medicinal product. For marketed medicinal products, this also includes failure to produce expected benefits (i.e. lack of efficacy), abuse or misuse.

Examples of an AE **include**:

- Exacerbation of a chronic or intermittent pre-existing condition including either an increase in frequency and/or intensity of the condition.
- New conditions detected or diagnosed after investigational product administration even though it may have been present prior to the start of the study.
- Signs, symptoms, or the clinical sequelae of a suspected interaction.
- Signs, symptoms, or the clinical sequelae of a suspected overdose of either investigational product or a concomitant medication (overdose per se will not be reported as an AE/SAE).
- "Lack of efficacy" or "failure of expected pharmacological action" per se will not be reported as an AE or SAE. However, the signs and symptoms and/or clinical sequelae resulting from lack of efficacy will be reported if they fulfill the definition of an AE or SAE.

Examples of an AE **does not** include a/an:

- Medical or surgical procedure (e.g. endoscopy, appendectomy); the condition that leads to the procedure is an AE.
- Situations where an untoward medical occurrence did not occur (social and/or convenience admission to a hospital).
- Anticipated day-to-day fluctuations of pre-existing disease(s) or condition(s) present or detected at the start of the study that do not worsen.
- The disease/disorder being studied, or expected progression, signs, or symptoms of the disease/disorder being studied, unless more severe than expected for the subject's condition.

## 9.2. Definition of a SAE

A serious adverse event is any untoward medical occurrence that, at any dose:

- a. Results in death
- b. Is life-threatening

NOTE: The term 'life-threatening' in the definition of 'serious' refers to an event in which the subject was at risk of death at the time of the event. It does not refer to an event, which hypothetically might have caused death, if it were more severe.

c. Requires hospitalization or prolongation of existing hospitalization

NOTE: In general, hospitalization signifies that the subject has been detained (usually involving at least an overnight stay) at the hospital or emergency ward for observation and/or treatment that would not have been appropriate in the physician's office or out-patient setting. Complications that occur during hospitalization are AEs. If a complication prolongs hospitalization or fulfills any other serious criteria, the event is serious. When in doubt as to whether "hospitalization" occurred or was necessary, the AE should be considered serious.

- d. Hospitalization for elective treatment of a pre-existing condition that did not worsen from baseline is not considered an AE.
- e. Results in disability/incapacity,

NOTE: The term disability means a substantial disruption of a person's ability to conduct normal life functions. This definition is not intended to include experiences of relatively minor medical significance such as uncomplicated headache, nausea, vomiting, diarrhea, influenza, and accidental trauma (e.g. sprained ankle) which may interfere or prevent everyday life functions but do not constitute a substantial disruption.

- f. Is a congenital anomaly/birth defect
- g. Medical or scientific judgment should be exercised in deciding whether reporting is appropriate in other situations, such as important medical events that may not be immediately life-threatening or result in death or hospitalization but may jeopardize the subject or may require medical or surgical intervention to prevent one of the other outcomes listed in the above definition. These should also be considered serious. Examples of such events are invasive or malignant cancers, intensive treatment in an emergency room or at home for allergic bronchospasm, blood dyscrasias or convulsions that do not result in hospitalization, or development of drug dependency or drug abuse.

Any abnormal laboratory test results (haematology, clinical chemistry, or urinalysis) or other safety assessments (e.g., ECGs, radiological scans, vital signs measurements), including those that worsen from baseline, and felt to be clinically significant in the medical and scientific judgement of the investigator are to be recorded as AEs or SAEs.

However, any clinically significant safety assessments that are associated with the underlying disease, unless judged by the investigator to be more severe than expected for the subject's condition, are **not** to be reported as AEs or SAEs.

#### Additional protocol defined criteria:

- All grade 4 laboratory abnormalities
- Any signs or symptoms of pneumonitis that are ≥ Grade 3 (NCI CTCAE) (defined as radiographic changes and requiring oxygen). Refer to NCI CTCAE grading of pneumonitis/pulmonary infiltrates.

Cardiovascular events have been seen in subjects taking other compounds that inhibit ErbB2 when used in combination with or following anthracyclines and interstitial pneumonitis has been reported in subjects taking compounds that inhibit ErbB1. As a precaution, the following will be reported as an SAE:

• Cardiac dysfunction will be reported as an SAE and will be defined as any signs or symptoms of deterioration in left ventricular ejection fraction (LVEF) that are Grade 3 or 4 (NCI CTCAE) or a ≥ 20% relative decrease in LVEF from baseline which is also below the institution's LLN. Refer to NCI CTCAE grading of left ventricular cardiac function.

#### As a precaution, the following will be reported as SAE:

- Cardiac dysfunction will be reported as an SAE and will be defined as any signs or symptoms of deterioration in LVEF that are Grade 3 (NCI CTCAE) or a 20% decrease in LVEF from baseline, and cardiac ejection fraction is below the institution's lower limit of normal. Refer to NCI CTCAE grading of left ventricular cardiac function.
- Any signs or symptoms of pneumonitis that are Grade 3 (NCI CTCAE) (defined as radiographic changes and requiring oxygen). Refer to NCI CTCAE grading of pneumonitis/pulmonary infiltrates.
- Hepatobiliary events have been seen in subjects taking lapatinib and other tyrosine kinase inhibitors. As a precaution, the following will be reported as an SAE:
  - ALT >3 × ULN and total bilirubin >2.0 × ULN (>35% direct; bilirubin fractionation required).

**NOTE**: bilirubin fractionation should be performed if testing is available. If testing is unavailable and a subject meets the criterion of total bilirubin  $>2.0 \times$  ULN, then the event should still be reported as an SAE.

Other hepatic events should be documented as an AE or an SAE as appropriate.

#### Treatment modification in case of cardiac dysfunction or interstitial pneumonitis

Subjects who have a  $\geq 20\%$  decrease in left ventricular cardiac ejection fraction relative to baseline, and the ejection fraction is below the institution's lower limit of normal, should have a repeat evaluation of ejection fraction 1-2 weeks later while still receiving Lapatinib. If the repeat ejection fraction evaluation confirms a  $\geq 20\%$  decrease in left ventricular cardiac ejection fraction, and the ejection fraction is below the institution's lower limit of normal, then treatment should be temporarily discontinued. If the left

ventricular ejection fraction recovers during the next 3 weeks, after consultation with GSK, the subject may be restarted on treatment. In such a case, Lapatinib dose-reduction is indicated. For such subjects, monitoring of left ventricular ejection fraction will then be performed 2 weeks and 4 weeks after re-challenge, and then every 4 weeks thereafter. If repeat ejection fraction evaluation still shows a decrease of  $\geq 20\%$  in left ventricular ejection fraction relative to baseline, and the value is below the institution's lower limit of normal, then the subject should be withdrawn from treatment.

Subjects with an NCI CTC AE Grade 3 or 4 left ventricular systolic dysfunction or interstitial pneumonitis must be withdrawn from treatment.

## 9.3. Disease-Related Events and/or Disease-Related Outcomes Not Qualifying as SAEs

An event which is part of the natural course of the disease under study (e.g., disease progression) does not need to be reported as an SAE. Progression of the subject's neoplasia will be recorded in the clinical assessments in the CRF. Death due to progressive disease is to be recorded on the 'Record of Death' CRF page and not as an SAE. However, if the progression of the underlying disease is greater than that which would normally be expected for the subject, or if the investigator considers that there was a causal relationship between treatment study drug or protocol design/procedures and the disease progression, then this must be reported as an SAE. Any new primary cancer must be reported as an SAE.

# 9.4. Lack of Efficacy

"Lack of efficacy" per se will not be reported as an AE. The signs and symptoms or clinical sequelae resulting from lack of efficacy will be reported if they fulfill the AE or SAE definition (including clarifications).

## 9.5. Expected side effects

**Rash:** Skin rash (usually grade 1-2) has been observed during the first several days of treatment with EGFR inhibitors and has been observed to diminish in severity after 4 weeks of treatment in many patients. In some patients, this rash appeared to be treatable with standard acne therapies, including topical and oral antibiotics used to treat acne. Anecdotal reports of improvement have occurred with several agents. In patients with severe rash, treatment may need to be discontinued or the dose reduced. Anecdotal reports of improvement have occurred with any of the following: minocycline, topical tetracycline, topical clindamycin, topical silver sulfadiazine, diphenhydramine, oral prednisone (short course).

**Diarrhea:** These broad general management principles are recommended to proactively try and avoid more serious complications by active management of diarrhoea syndrome. Guidelines such as these should never replace sound clinical judgement. Experience thus far suggests that when lapatinib is used as monotherapy, uncomplicated Grade 1 or 2

diarrhea is most prevalent. These general management principles do not address comprehensive management of more serious or protracted diarrhea syndromes.

Common clinical sense with the onset of uncomplicated Grade 1-2 diarrhea: stop all lactose containing products: drink 8-10 large glasses of clear liquids a day; eat frequent small meals; for Grade 2 diarrhea, consider a dose reduction of lapatinib (discuss with medical monitor); administer standard doses of loperamide: initial dose 4 mg followed by 2 mg every 4 hours or after every unformed stool. It is suggested to continue loperamide until the subject is free from diarrhea for 12 hours.

For Grade 3 or 4 diarrhea or Grade 1 or 2 with complicating features (severe cramping, severe nausea/vomiting, decreased performance status, fever, sepsis, Grade 3 or 4 neutropenia, frank bleeding, dehydration) use intravenous fluids as appropriate, consider hospital administration. Use prophylactic antibiotics as needed (example flouroquinolones) especially if diarrhea is persistent beyond 24 hours or there is a fever or Grade 3-4 neutropenia, hold both cytotoxic chemotherapy and lapatinib and discuss with medical monitor.

**Nausea:** Routine premedication for nausea is not necessary, but symptomatic patients should be treated with standard antinausea/antiemetic therapy as necessary.

If the patient vomits after taking the tablets, the dose is replaced only if the tablets can actually be seen and counted.

Cardiac function: please refer to Section 7.3.1

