## 7.3. Dose Adjustment, Delays and Dose Modifications

Subjects will be treated until disease progression or withdrawal from study due to unacceptable toxicity or consent withdrawal. Every 4-week period subjects will be evaluated for evidence of drug-related toxicity. Throughout the study, the following criteria will be used to evaluate toxicity in haematology, blood chemistry and any nonhematologic toxicity.

Non-Hematologic Toxicity	Any Grade 3 or 4 drug-related toxicity
Hematology	ANC is < 1.0 x 109/L
	Platelet count is < 75.0 x 109/L
Chemistry	Unresolved grade 3 or 4 toxicity (except bilirubin)
	See Section 7.3.2 for liver function test abnormalities
Serum Creatinine and Calculated	≥2.0 mg/dL
Creatinine Clearance 	≤ 25 mĽ/min

Treatment will be **delayed if**:

1. Calculated by the Cockcroft and Gault Method

Treatment may be delayed up to 2 weeks, to allow for resolution of toxicity except in the event of NCI CTCAE Grade 3 and 4 Left Ventricular Cardiac Dysfunction or NCI CTCAE Grade 3 and 4 interstitial pneumonitis, *events that require patient's withdrawal*. The investigator must consult with the Study Medical Monitor prior to continuing therapy for any subject requiring a delay of more than 2 weeks for unresolved toxicity, but in general, such subject should be withdrawn from the study.

If treatment is delayed for reasons other than toxicity (i.e. unplanned travel or vacation, or lack of transportation to the site) and the subject has insufficient investigational product available, the subject should resume the usual dosing schedule once the drug supply has been made available. However, if the subject has been off therapy for more than 2 weeks, the Investigator must consult with the Study Medical Monitor prior to continuing therapy.

Dose reduction for drug-related toxicity is permitted, however the Study Medical Monitor must be consulted prior to implementing any change in dosing. Once the dose has been reduced, subjects should not be rechallenged to a higher dose level. If a NCI CTCAE Grade 3 and 4 drug-related event (other than Left Ventricular Cardiac Dysfunction or Interstitial Pneumonitis) has occurred, the investigator may discuss with the GSK Medical Monitor whether a reduction of dose is appropriate.

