## Table 2Dose Reduction Criteria and Guidelines for Management of Iapatinib
Associated Toxicity

Toxicity	Grade	Guideline for Management	Lapatinib Dose Modification 
Diarrhea	1	stop all lactose containing products, drink 8-10 large glasses of clear liquids a day, eat frequent small meals	None
	2	Loperamide (4 mg at first onset, followed by 2 mg every 2–4 hrs until diarrhea free for 12 hrs)	Consider a dose reduction of lapatinib (discuss with medical monitor)
	≥ 3(despite optimal use of loperamide)		Hold until recovery to $\leq$ grade 1, up to 21 days  . And then reduce 1 dose level.
Rash	1 2 ≥ 3	No intervention Any of the following: minocycline  , topical tetracycline or clindamycin, topical silver sulfadiazine, diphenhydramine, oral prednisone (short course)	None None; If unacceptable to patient or medically concerning then hold until recovery to $\leq$ grade 1, up to 21 days  . Restart at same dose  . Hold until recovery to $\leq$ grade 1, up to 21 days  . And then reduce 1 dose level.
Other Toxicity (excluding left ventricular dysfunction	2	No Intervention Treatment as appropriate	None None; If unacceptable to patient or medically concerning then hold until recovery to $\leq$ grade 1, up to 21 days  . Restart at same dose  .
and pneumonitis, see below)	2 prolonged or clinically significant and grade $\geq 3$	Treatment as appropriate	Hold until recovery to < grade 1, up to 21 days and then reduce 1 dose level 

1. if no recovery after 2 weeks of holding drug, patients must be withdrawn from unless in the opinion of the investigator & GSK Medical Monitor, there is reason to believe that the patient is still experiencing clinical benefit.

2. if dose has been previously held for grade 2 toxicity and grade 2 symptoms recur, OR if the patient finds the symptoms unacceptable, hold dose until recovery to < grade 1 and then reduce dose one level

3. recommended dose: 200mg po bid (loading dose), followed by 100mg po bid for 7-10 days

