# 7.9. Concomitant Medications and Non-Drug Therapies

## 7.9.1. Permitted Medications and Non-Drug Therapies

All concomitant medications taken during the study will be recorded in the CRF. The minimum requirement is that drug name and dates of administration are to be recorded. In addition, indication and dose information should also be captured on the CRF, if possible. If there are any questions on medications not listed below, please contact the medical monitor of GSK for further information and clarification.

The following will be recorded on the appropriate CRF pages:

- A complete list of prescription and over-the-counter medications that have been taken within 4 weeks prior to the first dose of study drug.
- All concomitant medications taken while subjects are receiving study drug.

Subjects should receive full supportive care during the study, including transfusion of blood and blood products, and treatment with antibiotics, antiemetics, antidiarrheals, and analgesics, as appropriate. Refer to Section 9.5 for supportive care guidelines for diarrhea.

Concomitant treatments with bisphosphonates and/or radiotherapy are allowed for non target bone lesion(s) prior to enrollment.

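### Section 9.5 holds lapatinib for grade 1–2 diarrhoea with complicating features (most clearly fever), Table 2's diarrhoea rows do not, and Table 2 is silent on grade ≥3 diarrhoea before loperamide is optimised

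*Protocol*

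**What the plan says.** Three places in the current protocol text govern lapatinib during diarrhoea.

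- **Section 7.3, delay table.** Under non-haematologic toxicity, treatment is delayed for "Any Grade 3 or 4 drug-related toxicity". There is no loperamide condition.
- **Section 7.3, Table 2, diarrhoea rows.** Grade 1 is managed by "stop all lactose containing products, drink 8-10 large glasses of clear liquids a day, eat frequent small meals", with no change to lapatinib. Grade 2 receives loperamide, and the lapatinib column reads "Consider a dose reduction of lapatinib (discuss with medical monitor"). The grade ≥3 row, which holds lapatinib and then reduces it by one level, carries the qualifier "despite optimal use of loperamide".
- **Section 9.5, Diarrhea.** A separate paragraph opens "For Grade 3 or 4 diarrhea or Grade 1 or 2 with complicating features" and lists features that include fever, dehydration, frank bleeding and severe cramping. It ends with the instruction to "hold both cytotoxic chemotherapy and lapatinib and discuss with medical monitor".

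Two pointers lead to different places. The Section 7.3 text sends dose decreases for lapatinib-related toxicity to Table 2. Section 7.9.1 says: "Refer to Section 9.5 for supportive care guidelines for diarrhea".

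For loperamide after the first 4 mg, Table 2 gives 2 mg at intervals of two to four hours (grade 2 row). Section 9.5 gives "initial dose 4 mg followed by 2 mg every 4 hours or after every unformed stool" in its paragraph on uncomplicated grade 1–2 episodes.

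**The concern.** A site faced with a low-grade but complicated episode can open either Table 2 or Section 9.5, each with a pointer behind it, and find different lapatinib instructions. A site faced with a first grade 3 episode finds a delay in one part of Section 7.3. In Table 2 it finds only a row whose condition is not yet met.

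The event is not a rare one for this drug: Section 2.2 names diarrhoea as the serious adverse event most often reported with lapatinib. What is at stake is mainly patient safety and uniform conduct across about 15 centres in two countries. Secondarily, dose holds and reductions may partly reflect which section a site consulted. Holds also count towards the requirement in Section 11.3.1 that per-protocol subjects receive at least 75% of doses up to week 12, and that population serves the primary objective.

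**Working it through.** The protocol gives no figure to reproduce here; the check is a comparison of texts.

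**Step 1: scope of the Section 9.5 hold.** The hold clause follows a sentence about antibiotics that ends with three conditions (persistence beyond 24 hours, fever, grade 3–4 neutropenia) and is joined to it by a comma. Two readings are possible:

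- *Broad:* the hold applies to all grade 3–4 episodes and to grade 1–2 with any listed feature.
- *Narrow:* the hold applies only when one of those three conditions is present.

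Fever triggers the hold on both readings. Neutropenia does too, but Section 7.3 has its own delay for ANC below 1.0 × 10⁹/L, so it is not a clean test case. Fever is.

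**Step 2: the same episode under each text.**

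| Episode | Table 2, diarrhoea rows | Section 7.3 delay table | Section 9.5 |
|---|---|---|---|
| Grade 1 with fever | No change | Not triggered by the diarrhoea | Hold, both readings |
| Grade 2 with fever | Consider reduction; no hold | Not triggered by the diarrhoea | Hold, both readings |
| Grade 2 with dehydration or severe cramping, no fever or neutropenia, within 24 h | Consider reduction; no hold | Only if the accompanying event is itself grade 3–4 and drug-related | Hold on the broad reading only |
| Drug-related grade 3, loperamide not yet optimised | No row applies | Delay | Hold (broad); on the narrow reading only with one of the three conditions |

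The first two rows are a direct difference between Table 2's diarrhoea rows and Section 9.5. The third depends on how Section 9.5 is read. The fourth is a gap inside Section 7.3 itself and does not depend on Section 9.5.

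**Step 3: other routes to a hold in Table 2.** The Other Toxicity rows allow a hold for grade 2 events of medical concern. They direct one for prolonged or clinically important grade 2 events and for grade ≥3. Section 7.3 bases adjustments on the most severe toxicity present. Lapatinib-related dehydration or vomiting can therefore reach a hold by that route. A mild fever accompanying grade 1–2 diarrhoea need not.

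**Step 4: precedence.** The Section 7.3 text points to Table 2 and Section 7.9.1 points to Section 9.5. Nothing says which prevails.

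**Step 5: link to the per-protocol rule.** Assuming one dose per day, 12 weeks × 7 = 84 doses, and 75% of these is 63. A single 14-day hold leaves 70/84 = 83%. One hold of that length does not by itself remove a subject from the per-protocol population, so the effect on the primary analysis is likely to be limited.

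**The case against.** The strongest reply is that the texts can be read together. Section 9.5 presents itself as general guidance that does not displace clinical judgement, and Section 7.9.1 refers to it only for supportive care. Its advice for uncomplicated grade 1–2 diarrhoea closely matches Table 2, so Table 2 could be taken to cover uncomplicated cases and Section 9.5 to add the complicated ones. Table 2's grade 2 row and the Section 9.5 hold both involve the medical monitor, and Section 7.3 requires consultation before any change in dosing. This softens the conflict, but the protocol nowhere states that division, and Section 9.5 still instructs a hold where Table 2's diarrhoea rows give none.

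Four stronger readings are tempting and are not supported:

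- *Table 2 keeps a patient with febrile or dehydrating grade 2 diarrhoea on full dose.* It does not say so. It asks for a reduction to be considered with the medical monitor, and the Other Toxicity rows may lead to a hold.
- *Table 2 tells sites to continue lapatinib in a first grade ≥3 episode.* It is silent on that case. Section 7.3 delays, and Section 9.5 also addresses grade 3–4 with a hold.
- *The loperamide schedules differ about twofold.* Over the first 24 hours, two-hourly dosing gives 4 + 11 × 2 = 26 mg and four-hourly dosing gives 4 + 5 × 2 = 14 mg. But Table 2's range includes the four-hourly interval, at which the totals are equal, and Section 9.5 also allows dosing per unformed stool with no stated ceiling. A site dosing every four hours satisfies both.
- *The chemotherapy wording changes treatment.* Exclusion criterion 6 bars concurrent chemotherapy, so there is nothing to hold. It is an editorial leftover.

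**Conclusion.** The concern holds in limited form. For grade 1–2 diarrhoea with fever, Section 9.5 directs a hold on any reading while Table 2's diarrhoea rows do not. For the other complicating features the conflict depends on an ambiguous sentence, and some accompanying events may reach a hold through another row of Table 2. Separately, Table 2 has no instruction for diarrhoea of grade 3 or higher before loperamide is optimised, although the Section 7.3 delay table covers it when drug-related. The loperamide difference is minor.

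The size cannot be quantified from the protocol. A reader might turn to the 123 diarrhoea reports among 2620 serious adverse events in Section 2.2. Those figures span all phases of the lapatinib programme, including combination regimens, and do not show how often complicated low-grade diarrhoea would be handled differently here. They show why the event deserves a clear instruction, not how large the effect is. The conclusion rests on the current text alone and takes no view on which rule or schedule is right. This is an internal inconsistency that should be corrected; it does not threaten the design.

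**What to change.** Reconcile the Section 7.3 delay table, Table 2 and Section 9.5 into one diarrhoea instruction that:

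1. gives a single lapatinib action for grade 1–2 with complicating features and names the features that trigger it;
2. gives a single lapatinib action for a first episode of grade 3 or higher, stating whether prior loperamide matters;
3. re-punctuates or splits the Section 9.5 hold sentence so that its scope is plain;
4. uses the same loperamide wording in both places;
5. states which section prevails, with a matching cross-reference in Section 7.9.1;
6. removes the chemotherapy wording.

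Which rule and which schedule are kept is for the sponsor to decide on clinical grounds. The cost is wording changes in these sections and one table, with no added procedures, visits or patients.
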